5. SAMPLE SIZE DETERMINATION

INTREPID study [study 206854 China CSR GSK Document Number [2019N418769_00](#)] showed that in the real world setting 19% participants had early withdrawn from the Trelegy treatment prior to week 24. Considering the difference in the China clinical practice and study designs, it is assumed that 79% enrolled participants would complete 12 weeks of Trelegy treatment with no intercurrent events, 20% would have the intercurrent event of receiving a new COPD maintenance therapy, 1% would have the intercurrent event of treatment discontinuation.

Based on results from a few studies, i.e., IMPACT [[Lipson](#), 2018; study CTT116855 China CSR GSK Document Number [2018N356723_00](#)], INTREPID [study 206854 China CSR GSK Document Number [2019N418769_00](#)] and one randomized controlled trial (RCT) [[Bansal](#),

2021], it is assumed that a decrease of 2 in the primary endpoint at week 12 will be observed in this study with a common standard deviation of 7.

A sample size of 460 is planned. With the assumptions in Table 1 of the protocol, the sample size would be able to provide a half-width ranging from 0.64 to 0.73 for the 95% confidence interval (CI) of the inverse probability weighted mean of the change from baseline in CAT score at week 12 in the primary analysis under different missingness scenarios.

6. SUPPORTING DOCUMENTATION

6.1. Appendix 1 Study Population Analyses

Unless otherwise specified, the study population analyses will be based on the Full Analysis Set.

6.1.1. Participant Disposition

A summary of the number of participants in each of the participant level analysis set will be provided.

The participant disposition will be summarized for:

- Number of withdrawals leading to the screening failure, number of subjects in the screening, number of subjects having failed the screening, based on the Screened Analysis Set.
- Trelegy conclusion and the primary reason of the Trelegy discontinuation
- Study conclusion and the primary reason of the Study discontinuation

6.1.2. Demographic and Baseline Characteristics

The following demographic characteristics will be summarized:

- Age: continuous and also in the category of 18-<40, 40-<65, 65-<85 and >=85 ages. Age is derived using the date of the informed consent date. Day and Month of birth are imputed as 30 June.
- Sex: male, female
- Height: continuous
- Weight: continuous
- Body Mass Index (BMI): continuous, calculated as weight (kg)/[height (m)]².

The following baseline characteristics will be summarized:

- COPD History:
 - Year of COPD, derived using the date of the informed consent date, continuous and also in the category of <6 months, >=6 months to <1 year, >=1 to <5 years, >=5 to <10 years, >=10 to <15 years, >=15 to <20 years, >=20 to <25 years and >=25 years.
 - Number of severe COPD Exacerbation during the Past Year,
 - Number of moderate COPD Exacerbation during the Past Year,
 - Number of moderate/severe COPD Exacerbation during the Past Year, continuous and also in the category of 0, 1 and >=2.

- Existing COPD Maintenance Treatment: ICS/LABA, LAMA/LABA, Free combination of ICS, LAMA, LABA
- Medical history
 - The number and percentage of participants with each medical history condition
- Smoking history
 - Smoking status
 - Year of smoking
 - Average Number of Units Consumed Per Day
 - Number of Pack Years
- Physical examination: Normal, Abnormal - Not Clinically Significant, Abnormal - Clinically Significant
- Electrocardiogram (ECG): Normal, Abnormal - Not Clinically Significant, Abnormal - Clinically Significant

6.1.3. Protocol Deviation

Important protocol deviations will be summarized.

Protocol deviations will be tracked by the study team throughout the conduct of the study. These protocol deviations will be reviewed to identify those considered as important as follows:

- Data will be reviewed prior to freezing the database to ensure all important deviations are captured and categorised in the protocol deviations dataset.
- This dataset will be the basis for the summaries of important protocol deviations.

6.1.4. Prior and Concomitant Treatments

Prior and concomitant medication tables will be summarized by Anatomical Therapeutic Chemical (ATC) level 1 and ingredient for:

- Pre-treatment COPD Medications
- On-treatment COPD Medications
- Post-treatment COPD Medications
- Prior and Concomitant Non-COPD Medications

Multi-ingredient medications will be presented according to their combination ATC classification rather than the classification of the ingredients.

Prior and Concomitant Non-Drug Treatments will be summarized.

6.1.5. Trelegy Exposure and Compliance

The duration of Trelegy, the actual dose will be summarized.

A summary of overall compliance for Trelegy based on the exposure data will be produced. Overall compliance will be summarized using descriptive statistics as well as the categories <80%, 80%-105%, and >105%.

Trelegy Compliance (%) = [Total cumulative actual dose / Total cumulative scheduled dose] *100.

Number of subjects with treatment switch will be summarized.

6.2. Appendix 2 Data Derivations Rule

6.2.1. Study Period

Assessments and events will be classified according to the time of occurrence relative to the study intervention period.

Pre-treatment is defined as time prior to the first dose of Trelegy.

On-treatment is defined as time from first dose to last date of Trelegy.

Post-treatment is defined as any time post on-intervention window, i.e. > last dose date of Trelegy.

For AE, if the study period cannot be determined due to partial or missing data, the study period would be classified as “on-treatment”, unless the end date of the AE rules out this probability. Trelegy-related AEs are classified as “on-treatment”.

For COPD medications, a COPD medication may be classified into one or multiple categories of “pre-treatment”, “on-treatment” and “post-treatment” medication. If the study period cannot be determined due to partial or missing data, the medication would be classified into one or multiple categories of “pre-treatment”, “on-treatment” and “post-treatment” if it might satisfy the study period definition(s).

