2. OBJECTIVES

Primary Objective	Primary Outcome
The primary objective of this study is to evaluate the effectiveness of Trelegy on health status in patients with symptomatic COPD at week 12.	
 Change from baseline of CAT score at week 12
Secondary Objectives	Secondary Outcomes
to evaluate the effectiveness of Trelegy on dyspnea in patients with symptomatic COPD at week 12. to evaluate the effectiveness of Trelegy on lung function in patients with symptomatic COPD at week 12. to evaluate the proportion of patients achieving health status response with Trelegy. to evaluate the effectiveness of Trelegy on health status in patients with symptomatic COPD at week 4.	
 Change from baseline of Modified Medical Research Council (mMRC) at week 12 Change from baseline of pre-dose FEV₁ at week 12 Proportion of CAT responder (defined as ≥ 2 unit decrease from baseline) at week 12 Change from baseline of CAT score at week 4
Exploratory Objectives	Exploratory Outcomes
to evaluate the effectiveness of Trelegy on lung function in patients with symptomatic COPD	
 Change from baseline of Forced Vital Capacity (FVC), Forced Expiratory Flow at the 25 and 75% (FEF₂₅₋₇₅), Inspiratory Capacity (IC) at week 12
Safety Objective	Safety Outcomes
The safety objective is to collect the safety information of participants using Trelegy.	
 Trelegy related AEs SAEs AEs that lead to the discontinuation of Trelegy

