4.5.1. Adverse Events

AE terms will be coded using Medicinal Dictionary for Regulatory Activities (MedDRA) dictionary.

The number and percentage of participants experiencing at least one AE of below category will be summarized:

- Overview of AEs
- On-treatment AEs will be summarized by system organ class (SOC) and preferred term (PT) for:
 - Trelegy related non-serious AE
 - SAEs
 - Trelegy related SAEs
 - AE leading to discontinuation of Trelegy
 - Trelegy related AE leading to discontinuation of Trelegy
- Post-treatment AEs will be summarized for:
 - SAEs by SOC and PT

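### An unrelated adverse event that starts after the last dose date and stops Trelegy is missing from the SOC/PT table of discontinuation events

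*SAP*

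**What the plan says.** Protocol section 2 names three safety outcomes, one of which is "AEs that lead to the discontinuation of Trelegy". The Table 1 notes ask sites to record these AEs whatever the investigator's view of causality. They also say that an AE unrelated to both treatment and discontinuation is not recorded unless it is serious. The safety paragraph of Protocol 3.8.2.2 promises the number and percentage of participants with such an event and sets no time limit.

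SAP 6.2.1 sets the periods: "On-treatment is defined as time from first dose to last date of Trelegy", and "Post-treatment is defined as any time post on-intervention window, i.e. > last dose date of Trelegy". It makes two exceptions for AEs. First, "Trelegy-related AEs are classified as" on-treatment, with no date condition. Second, "For AE, if the study period cannot be determined due to partial or missing data, the study period would be classified as" on-treatment, unless the AE's end date rules that out.

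SAP 4.5.1 first lists an overview of AEs, without describing its content. It then says "On-treatment AEs will be summarized by system organ class (SOC) and preferred term (PT) for" a list that includes "AE leading to discontinuation of Trelegy". The line that begins "Post-treatment AEs will be summarized for" is followed by SAEs only. SAP 4.8, on changes from the protocol, discusses only the sensitivity analysis.

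**The concern.** The reason for stopping treatment can easily come after the last dose. Protocol 3.5.1 has participants inhale one dose each morning. If something happens during the night and the next dose is never taken, the onset date is the day after the last dose date. The same holds for an event that starts during a pause in dosing which then becomes permanent.

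The SAP's on-treatment filter removes such an event from the table built to show it. The override for related AEs means that only unrelated events can be lost, yet the protocol took care to include unrelated events in this outcome. Under the Table 1 notes, a non-serious unrelated AE is generally collected only because it led to stopping. For that event the discontinuation table is the only SOC/PT table it could enter.

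At stake is the completeness of a named safety outcome in a study that Protocol 3.8.3 says is meant to support licence renewal.

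**Working it through.** The plan gives no figure to reproduce on this point, so the check applies the period rules in SAP 6.2.1 and then the table rules in SAP 4.5.1 to an AE that leads to stopping Trelegy. SAP 6.2.1 classifies events by time of occurrence; this is read as onset, which fits the use of the AE start date in SAP 6.4.

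| AE leading to discontinuation | Period under SAP 6.2.1 | In SOC/PT discontinuation table? | In any other SOC/PT table? |
|---|---|---|---|
| Onset on or before the last dose date (after first dose) | On-treatment | Yes | Yes, if related or serious |
| Onset after last dose date, related | On-treatment (override) | Yes | Yes, the related-AE tables |
| Period undeterminable because dates are partial or missing | On-treatment by default, unless the end date rules it out | Yes | Yes, if related or serious |
| Onset after last dose date, fully dated, unrelated, serious | Post-treatment | **No** | Post-treatment SAE table only |
| Onset after last dose date, fully dated, unrelated, non-serious | Post-treatment | **No** | **None** |

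Only the last two rows lose the event from the discontinuation table, and only the last row loses it from every SOC/PT table.

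Set against the protocol, both rows conflict with it. Table 1 collects these events regardless of causality, and 3.8.2.2 counts them regardless of period. SAP 4.8 does not list the on-treatment restriction as a departure.

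The rules also treat like events unevenly. A fully dated unrelated event on the day after the last dose is excluded, while the same event with its dates missing is kept by default.

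On size, the nearest planning figure is all-cause. Protocol 3.7.1 assumes 20% receive a new maintenance therapy, which SAP 4.2.2 defines as having discontinued Trelegy and switched, and 1% stop otherwise. That is 460 × (0.20 + 0.01) = 96.6, or about 97 participants who stop Trelegy for any reason. The documents do not say how many stop because of an AE, how many of those AEs start after the last dose date, or how many are judged unrelated. The number affected is the product of these, and none of the three is given.

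**The case against.** The best case for leaving the plan alone is that little is lost. Serious events still appear by SOC and PT, only in the post-treatment table. The overview of AEs stands outside the on-treatment line and may count every discontinuation AE. SAP 6.1.1 summarises the primary reason for stopping Trelegy, which does not depend on AE onset. Protocol 3.8.2.2 still promises the overall count, and SAP 4.8 withdraws nothing.

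Part of this stands. It is not shown that the outcome is undercounted in every output; the shown loss is in the SOC/PT tables. But the SAP does not say what the overview contains or which period it covers, the disposition summary carries no preferred terms, and a post-treatment SAE table does not show that the event ended treatment.

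Three stronger readings are tempting and are not supported:

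- A reader might infer that any AE starting the day after the last dose is dropped. SAP 6.2.1 keeps related AEs, and AEs of undetermined period, on-treatment.
- A reader might put the loss at 2 to 5 participants: assume 1–3% of 460 stop for an AE (about 5 to 14), assume dosing at 08:00 so that 8/24 = one third of onsets fall on the next date, and take one third of 5 to 14. That applies one third to all AE discontinuations. It belongs only to AEs that begin between the last dose and the next one due, and related AEs must be removed. If each of those two shares is 25–50% (assumed), the result is 5 × 0.25 × 1/3 × 0.25 = 0.1 to 14 × 0.50 × 1/3 × 0.50 = 1.2 participants. This ignores onsets during longer pauses. Every input except 460 is an assumption, so the range shows only that the number is likely small.
- A reader might infer that the licence-renewal data understate harm from Trelegy. Every affected event was judged unrelated by the investigator, and affected SAEs change table rather than vanish.

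**Conclusion.** The point holds in a narrow form. An AE that leads to discontinuation, is judged unrelated and has a determinable onset after the last dose date is left out of the SOC/PT discontinuation table. It is in no SOC/PT table if non-serious, and only among post-treatment SAEs if serious. This departs from Protocol 3.8.2.2 and the Table 1 collection rule, and the SAP does not declare it.

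The conclusion rests on reading time of occurrence as onset and on an overview of AEs that is not specified. The size cannot be derived from the documents; it is probably very small and could be zero. The change is still worth making because a stated rule gives an incomplete table for a named safety outcome, and the repair costs almost nothing.

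**What to change.** Either of two changes is enough:

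1. In SAP 6.2.1, extend the existing override so that AEs leading to discontinuation of Trelegy, like related AEs, are classified as on-treatment.
2. In SAP 4.5.1, tabulate all AEs flagged as leading to discontinuation regardless of study period, which is what Protocol 3.8.2.2 describes.

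Both also cover an onset several days after the last dose. It would help to state what the overview of AEs counts and over which period. The rule chosen should apply both to the licence-renewal analysis in SAP 4.7, if it is performed, and to the whole-study analysis.

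Adding a day to the on-treatment window is not advised. It would miss later onsets, and the same periods classify COPD medications for SAP 6.1.4, so a replacement therapy begun the day after the last Trelegy dose would become an on-treatment medication and blur the switch.

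The cost is one sentence in the SAP and its programming, with no new data and no effect on the effectiveness analyses. Discontinuation AE counts may rise slightly. Under the first option the affected SAEs also move from the post-treatment to the on-treatment table; under the second the SAE tables stay as they are.

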6.3. Appendix 3 Assessment Windows

6.3.1. General

In general, data will be reported according to the nominal time of clinic visits and assessments as specified in the protocol.

6.3.2. E.D. Data

To make full use of effectiveness outcomes data, the effectiveness measurements collected at E.D. including CAT score, mMRC and Pulmonary function test (Pre-dosed FEV₁, FVC, FEF₂₅₋₇₅ and IC) will be used according to the following rules:

- If E.D. date of the participant is before Day 55 ($<=55$), the participant's value of week 12 related endpoints will be treated as missing and its analysis approach can be found in Section 4. Otherwise, the participant's value of week 12 related endpoints will be mapped to E.D. results.
- If E.D. date of the participant is before Day 12 ($<=12$), the participant's value of week 4 related endpoints will be treated as missing and its analysis approach can be found in Section 4. Otherwise, the participant's value of week 4 related endpoints will be mapped to E.D. results, if E.D. date of the participant is before Day 21 ($<=20$).

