3.1. Study Design

This is a 12-week, prospective, open label, single cohort study. The enrolled participants will be those who are symptomatic under COPD maintenance treatments, and newly prescribed with Trelegy under the discretion by clinical physicians.

The study applies a single cohort design to evaluate the effectiveness following 12-week treatment with Trelegy by comparison to baseline data, which can reflect the benefits (i.e., CAT score and FEV₁, etc.) of patients who remain symptomatic with their prior maintenance treatment. The decision to prescribe Trelegy shall be independent to the study with medical records providing documentation of a Trelegy prescription.

The prospective data collection starts from Visit 1 when Trelegy is taken by patients for the first dose (see [Figure 1](#) below). The participants will complete the CAT score at Visit 1, Visit 2 and Visit 3 or early discontinuation/withdrawal visit (E.D.), and the mMRC at Visit 1 and Visit 3 or E.D. The participants' pulmonary function test will be assessed at Visit 1 and Visit 3 or E.D.. The investigators will record Trelegy-related adverse events (AEs), serious adverse events (SAEs) and AEs that lead to withdrawal from Trelegy.

Figure 1 The Schematic diagram for this study

* : V0 and V1 could occur on the same day, and V1 should be completed ≤7 days after V0.

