3.2. Data Source / Data Collection

The investigators will enroll participants by assessing the inclusion/exclusion criteria. The patients will be enrolled at visit 1 and will be followed up prospectively for 12 weeks.

During this trial the following information and measurements will be collected, and the details are listed in [Table 1](#):

To be completed at Visit 1:

- Patient demographics (including sex, age, height, weight)
- Patient past medical history and co-morbid diseases
- Patient smoking history [never a smoker, former smoker (previously smoked ≥ 10 pack year and has not smoked for at least 6 months prior to Visit 1), current smoker (10 pack year and smoked within 6 months prior to Visit 1); the number of pack years for former smoker and current smoker should be calculated (round up to the nearest integer)]
- Patient concomitant medication
- Pregnancy status
- Oxygen saturation
- Patient vital signs and Electrocardiogram (ECG)
- CAT score
- mMRC
- Pulmonary function test (spirometry): pre-dose FEV1, FVC, FEF₂₅₋₇₅ and IC
- Trelegy related AEs
- AEs that lead to the discontinuation of Trelegy
- SAEs

To be completed at Visit 2:

- Patient concomitant medication
- Pregnancy status
- Number of doses of Trelegy taken
- CAT score
- Trelegy related AEs
- AEs that lead to the discontinuation of Trelegy
- SAEs

To be completed at Visit 3 or E.D.:

- Patient concomitant medication
- Pregnancy status
- Number of doses of Trelegy taken
- Patient vital signs
- CAT score
- mMRC
- Pulmonary function test (spirometry): Pre-dosed FEV₁, FVC, FEF₂₅₋₇₅ and IC
- Trelegy related AEs
- AEs that lead to the discontinuation of Trelegy
- SAEs

Table 1 Visit flow chart and data collection schedule

Procedure	Conse nting	Treatment and Observation Period (Days)			E.D.	Notes E.D. = early discontinuation / withdrawal (within 7 days of study discontinuation)
Study visit	V0 ¹ Pre- Scree ning	V1 Screen, enroll & baseline (Day 1)	V2 (Day 28)	V3 End of Study (Day 84)		
Time Window Allowed (days)			±7	±10		
Informed consent ²	X					
Inclusion / exclusion criteria		X				
Demography		X				
Full physical examination including height and weight		X				
Smoking History		X				

Procedure	Conse nting	Treatment and Observation Period (Days)				Notes E.D. = early discontinuation / withdrawal (within 7 days of study discontinuation)
Medical history: past and current medical conditions		X				
Vital signs		X		X	X	
Oxygen saturation		X				
ECG		X				

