3.2.1. Withdrawal from Trelegy or the Study

Participants that permanently stop Trelegy are not required to withdraw from the study. If for any reason a participant must permanently stop Trelegy, every effort should be made by the Investigator/delegate to keep the participant in the study to collect all the effectiveness and safety data of the subsequent visits per the Schedule of Activities (SoA) after the Trelegy discontinuation.

Any female participant who becomes pregnant while participating will be withdrawn from the study.

A participant may withdraw from the study at any time at his/her own request, or may be withdrawn at any time at the discretion of the investigator for safety, behavioural, or administrative reasons. If a participant withdraws from the study, he/she has to complete the E.D. visit per SoA ([Table 1](#)), and no more extra data will be collected after E.D. visit.

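### SAP 6.3.2 leaves an E.D. CAT from Days 21–35, the protocol's own Visit 2 window, unused for week 4 even when no Visit 2 CAT exists (minor)

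*SAP*

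**What the plan says.** SAP 6.3.2 sets out how effectiveness measurements from the early discontinuation (E.D.) visit enter the analysis. Its stated aim is "To make full use of effectiveness outcomes data". Two rules follow.

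- Week 12: missing if the E.D. date is up to Day 55 (bracketed limit); otherwise the E.D. result is used.
- Week 4: missing if the E.D. date is up to Day 12 (bracketed limit); otherwise "mapped to E.D. results, if E.D. date of the participant is before Day 21".

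Nothing further is said about week 4 for an E.D. visit from Day 21 on. SAP 6.3.1 adds only that, in general, "data will be reported according to the nominal time of clinic visits and assessments as specified in the protocol".

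Protocol Table 1 places Visit 2 at Day 28 with a tolerance of 7 days either way. It gives E.D. a separate column and describes it as "early discontinuation / withdrawal (within 7 days of study discontinuation". Protocol 3.2.1 states that after withdrawal from the study "no more extra data will be collected after E.D. visit". CAT is the only effectiveness measure scheduled at Visit 2, so the week-4 rule matters for CAT alone.

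**The concern.** The Day 20 cut-off ends exactly where the Visit 2 window begins. It probably presumes that from Day 21 a Visit 2 CAT will be on file. The SAP does not state this, and the protocol does not guarantee it. Where no Visit 2 CAT exists, the rule keeps a CAT taken well before the window and drops one taken inside it, contrary to the section's aim.

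The week-4 change from baseline has three uses: as a secondary endpoint (SAP 4.3.1), as a weighted record in the MMRM, and as a covariate in the logistic model behind the week-12 weights (both SAP 4.2.2). For the participants in question, the E.D. CAT is the only post-baseline CAT. Without it they have no observed post-baseline record in the MMRM at all.

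**Working it through.** The plan gives no figure for this rule, so the check sets its day limits against the visit schedule.

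**Inputs.** Visit 2 at Day 28 ± 7, and E.D. up to 7 days after study discontinuation (Protocol Table 1). Week-4 limits of ≤12 and ≤20, and week-12 limit of ≤55 (SAP 6.3.2, bracketed symbols). Planned N = 460 (Protocol 3.7.2).

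**Visit 2 window.** 28 − 7 = Day 21 to 28 + 7 = Day 35, which is 35 − 21 + 1 = 15 days.

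**Use of an E.D. CAT by E.D. date, when no Visit 2 CAT exists:**

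| E.D. date | Week 4 | Week 12 | Position |
|---|---|---|---|
| Up to Day 12 | missing | missing | before window |
| Days 13–20 | E.D. CAT used | missing | before window |
| Days 21–35 | not mapped | missing | inside window |
| Days 36–55 | not mapped | missing | after window |
| Day 56 on | not mapped | E.D. CAT used | after window |

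All 15 days of the Visit 2 window fall in the row where the CAT serves neither time point.

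**Distance from Day 28.** Days 13–20 are 28 − 13 = 15 to 28 − 20 = 8 days early, and are used. Days 21–35 are at most 7 days away, and are not.

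**Can the case occur?** There are two routes.

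1. The participant leaves before the window opens. Leaving on Day 14 allows E.D. as late as 14 + 7 = Day 21; leaving on Day 20 allows 20 + 7 = Day 27. So leaving on Days 14–20 can give an E.D. visit on Days 21–27.
2. The participant leaves on Days 21–35 before attending Visit 2, with E.D. also inside the window.

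In both, data collection ends with E.D., so no later visit fills the gap.

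**Does another section settle it in favour of use?** SAP 6.3.1 works by nominal visit. E.D. has its own column in Table 1, and Protocol 3.6.1.1 pairs it with Visit 3, so nominal reporting does not turn an E.D. record into a week-4 record.

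**Size.** The documents give no distribution of E.D. dates, so the number affected cannot be derived. Each such participant is 1/460 = 0.22% of the planned sample at week 4.

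**The case against.** The strongest reply is that the SAP does give an answer. The mapping is conditional on the E.D. date, so from Day 21 the E.D. result is simply not mapped. Week 4 is then the Visit 2 CAT if there is one and missing if not. Missing week-4 values have their own weight model (SAP 4.3.1), and a missing covariate may be imputed (SAP 4.2.2). The full-use aim is also qualified by the rules listed under it. This stands as a reading of the text, and it means the two bullets do not contradict each other. It does not answer the point: on this reading the rule discards a collected CAT from the scheduled week-4 window and leaves weighting or imputation to stand in for it.

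Other replies stand in part.

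- The affected group is narrow. A missed visit is to be rescheduled (Protocol 3.2.2), and a Visit 2 CAT may be taken remotely (Table 1, note 2). A participant who comes in on Days 21–35 to leave the study might be recorded under Visit 2, E.D. or both; the documents do not show how.
- Any date cut-off separates people who left on the same day. Such comparisons are therefore no argument against Day 20 in particular, and none is relied on here.
- Extending the mapping to Day 35 still leaves an asymmetry: Days 13–20 are used, while Days 36–42, which are 8–14 days late, are not. That is true. The proposed limits are the SAP's existing lower limit and the end of the protocol window; they are not claimed to be optimal.

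A reader might infer that everyone who stops treatment early loses the week-4 value. The documents do not support this. Protocol 3.2.1 says "Participants that permanently stop Trelegy are not required to withdraw from the study", so those who stay on can attend Visit 2. Those lost to follow-up without an E.D. visit have no E.D. CAT to use.

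**Conclusion.** The point holds as a minor one. For an E.D. visit on Days 21–35 with no Visit 2 CAT, the SAP as written uses the E.D. CAT for neither week 4 nor week 12, while an earlier CAT from Days 13–20 is used. This rests on a literal reading of SAP 6.3.2, on the bracketed limits, and on the Table 1 windows.

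The number affected is probably small and cannot be derived. A reader might infer that the week-4 mean or the primary week-12 result is biased. The documents do not support that: they say nothing on how many such participants there would be or how their scores would differ. Week-12 values do not change directly, and any effect through the MMRM or the weight model is unquantified. The study has no formal hypothesis tests (SAP 2), and the planned sample size and precision are untouched.

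Separately, words and symbols in SAP 6.3.2 differ by one day at Day 12 and at Day 55; at Day 20/21 they agree. The Day 55 mismatch decides whether an E.D. CAT on that day counts as the week-12 primary value, so it needs settling too.

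**What to change.** Replace the second bullet of SAP 6.3.2 with:

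> If a Visit 2 CAT exists, it is the week-4 value. If none exists and the E.D. date is on Days 13–35, the E.D. CAT is the week-4 value. Otherwise the week-4 value is missing.

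This never overwrites a Visit 2 CAT, settles which record counts when both exist, and gives every E.D. date a stated week-4 status.

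Then make words and symbols agree. If the symbols are meant, write on or before Day 12 and on or before Day 55. If the words are meant, the week-4 range above becomes Days 12–35 and the week-12 limit becomes ≤54, with every sentence changed to match.

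The cost is one SAP bullet, the two wording corrections and one line of derivation code. No new data are needed.
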